10.3 Premature Termination of Study/Closure of Site

The Institution has the right to close this study, and the physician has the right to stop recruitment, at any time.

11 STATISTICAL METHODS

In addition to statistical analysis described herein, the data may be reviewed intermittently to detect safety or efficacy signals in real time. Since this is an observational study, this data access will not affect the formal statistical analysis to be completed at the end of the study.

The statistical analysis will be performed separately in each study cohort to take into account the different endpoints defined for each study cohort. Also, within each study cohort, the analysis will include a descriptive comparison of the siltuximab treatment group and the control group with respect to the endpoints and other measurements.

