8 OBSERVATIONAL PLAN

8.1 Overall Study Design and Plan – Description

This is a single-center, observational case control study in Italy that follows the use of treatment siltuximab in patients diagnosed with COVID-19 infection who have developed serious respiratory complications. Retrospective data collection will be carried out on patients who have received the drug through the compassionate use program. (this program is still ongoing, and enrolling patients).

Patients receiving siltuximab will be included into this observational study and will be divided into 2 cohorts, split in an approximate 3:1 ratio: 75% will be in Cohort A and are not in an ICU setting and are not on mechanical ventilation, while 25% will form Cohort B and consists of patients in an ICU setting who are receiving invasive ventilation.

[figure not shown]
Each patient will be matched to a consented case control receiving treatment other than siltuximab for their condition.

Match Criteria

Patients receiving siltuximab and controls will be matched according to the following criteria:

- Age (by decades)
- Sex (M/F)
- P/F fraction (<100, 100-150 or >150) at baseline
- Antiviral therapy

Figure 1: Study Design

Procedures outlined in this protocol are based on the compassionate use program, where patients are managed as per clinicians' best judgement and best practice. No procedures are required by this observational protocol. Data on the procedures already performed during the routine diagnosis and treatment of COVID-19 patients will be collected. The list of clinical and laboratory parameters is provided to direct data collection for this observational study (as available in the medical records).

During their hospitalization, patients will be monitored as per standard hospital practice or as per national (emergency) guidelines in accordance with extraordinary circumstances relating to the COVID-19 outbreak. After discharge, patients will be asked to provide (from their primary health care providers) relevant laboratory results for 30 days following start of COVID-19 treatment via ventilation (either mechanical or non-invasive).

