11.1 Sample Size Determination

No statistical sample size estimation was performed. For this study patients from one single center in Italy will be enrolled as follows:

- All patients treated with siltuximab diagnosed with COVID-19 infection who have developed serious respiratory complications, and
- An equal number of case control patients that consented to their data collection.

It is estimated that in total up to 50 patients will be enrolled.

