11.2.5 Ad hoc Analysis

As soon as any relevant data has been recorded and based on the physician's decision on the basis of public interest, ad hoc analyses will be prompted, and information released in a timely manner.

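### Observational status does not make real-time efficacy review harmless, and ad hoc release carries no follow-up condition although the primary endpoints include 30-day mortality

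*Protocol*

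**What the plan says.** Protocol section 11 states that "the data may be reviewed intermittently to detect safety or efficacy signals in real time". It then gives an assurance, for which the only reason offered is that the study is observational: "this data access will not affect the formal statistical analysis to be completed at the end of the study".

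Three other provisions bear on that assurance.

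- **Ad hoc analysis (11.2.5).** The trigger is "As soon as any relevant data has been recorded". On the physician's decision and in the public interest, "ad hoc analyses will be prompted, and information released in a timely manner". No minimum follow-up or data cut is named.
- **Stopping (10.3).** "the physician has the right to stop recruitment, at any time", with no criterion attached.
- **Controls (8.1).** "Each patient will be matched to a consented case control receiving treatment other than siltuximab for their condition". Matching is 1:1 on age decade, sex, P/F band and antiviral therapy. Data come from existing medical records.

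Data are recorded for 30 days from first ventilation (10.1.1). Both cohorts' primary endpoints include 30-day mortality (section 6). The compassionate use programme is still enrolling (8.1).

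**The concern.** Observational status means that the protocol allocates no treatment, so a look at the data cannot disturb a protocol allocation. It does not protect the other routes by which knowledge of outcomes can enter a comparison: which eligible untreated patient becomes the control, and when recruitment ends. Either can move the final siltuximab-versus-control difference, whether or not it is tested.

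Early release is a separate matter. A 30-day endpoint read before day 30 undercounts events. If the undercount falls more heavily on the siltuximab group, the drug looks better than it is. At stake are the descriptive contrast that section 11 plans within each cohort and any early public message drawn from it.

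**Working it through.** The protocol gives no event rate, alpha, power or stopping rule, so there is no figure to reproduce. Every rate, look and stopping rule below is an assumption.

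**1. Early release with unequal follow-up (bears on 11.2.5 only).** Let R be the 30-day risk, equal in both groups, with constant hazard. The expected proportion with an event by day t is F(t) = 1 − (1 − R)^(t/30). Controls are followed for 30 days and siltuximab patients for t days.

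| R | t | F(t) | Gap, R − F(t) |
|---|---|---|---|
| 50% | 10 | 1 − 0.5^(10/30) = 20.6% | 29.4 points |
| 50% | 14 | 1 − 0.5^(14/30) = 27.6% | 22.4 points |
| 20% | 10 | 1 − 0.8^(10/30) = 7.2% | 12.8 points |
| 20% | 14 | 1 − 0.8^(14/30) = 9.9% | 10.1 points |

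With equal follow-up in the two groups the gap is zero at any R. The hazard shape matters: if 80% of events fell in the first 10 days, then at R = 50% the day-10 proportion would be 0.8 × 50 = 40%, and the gap 10 points.

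**2. Stopping after seeing results (bears on the final analysis).** Up to 50 patients at 1:1 gives 25 treated, of whom 75% (25 × 0.75 = 18.75, about 19) are in Cohort A. Simulation used 19 against 19, equal true event rates from 0.3 to 0.6, and 200,000 runs per rate. Recruitment was assumed to stop once the observed risk difference reached −0.20 or better.

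- Two looks (at 10 and 19 pairs): the mean reported difference is about −0.03 instead of 0.
- Four looks (at 5, 10, 15 and 19 pairs): about −0.09 to −0.10.
- The chance of reporting −0.20 or better is 11–13% with a fixed size, 26–28% with two looks and 44–46% with four.

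**3. Outcome-aware choice of control (bears on the final analysis).** Suppose that in a fraction f of pairs two controls are eligible and one with an event is taken if there is one. The control rate becomes (1 − f)p + f[1 − (1 − p)²], so the bias in the risk difference is −f·p(1 − p). At p = 0.3 and f = 0.1 this is −0.021; at p = 0.5 and f = 0.5 it is −0.125.

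**4. A tempting remedy that fails.** Suppose a release admitted patients who had either reached day 30 or died. At a 50% 30-day risk of death, of 100 patients with 10 days elapsed, 20.6 would have died and be admitted, and 79.4 would be alive and excluded. The recent patients admitted would all be deaths. Eligibility for a release must therefore depend on elapsed time, not on outcome.

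**The case against.** The study is hypothesis-generating (8.2) and exploratory (11.2). Section 11 plans only a descriptive contrast, and 11.2.3 says that the groups will not be compared statistically on endpoints. No alpha is stated, so a claim of inflated type I error would have no basis. All siltuximab patients are to be entered (11.1), which limits selection on the treated side. The right to stop in 10.3 is a general one, and nothing ties it to efficacy review. A control-selection algorithm may stand in an analysis plan that is not shown. All of this stands and limits the consequences, but a descriptive difference can still be biased. The point against section 11 is that it makes a positive assertion on a reason that does not carry it.

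Four stronger readings are tempting and are not supported.

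- **That the physicians who see outcomes choose the controls.** The matching text names no selector. Section 10.1.2 has the physician inform and seek consent from a patient already identified. No section says who carries out the real-time review.
- **That results will be released before follow-up is complete.** Section 11.2.5 permits this but does not plan it, and it does not say that a release will compare siltuximab with controls.
- **That consent rules differ between the groups.** Section 11.1 lists all siltuximab patients beside "An equal number of case control patients that consented to their data collection". However, 13.4 requires consent for each patient, and the doctor's emergency form (10.1.2, 13.4) and the deceased-patient provision (9.1.1) are not limited to treated patients.
- **That the 22 to 29 point gap is a bias in the final analysis.** It vanishes once both groups have 30 days. No section says that controls enter earlier or are followed longer than siltuximab patients.

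**Conclusion.** The concern holds in a limited form. The assurance in section 11 does not follow from the study being observational, because control choice and the end of recruitment remain open to knowledge of outcomes. Under the assumed scenarios, stopping shifts a true zero difference by about −0.03 to −0.10, and outcome-aware control choice shifts it by about −0.02 to −0.13. These figures show what could happen, not what the protocol says will happen.

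Separately, 11.2.5 sets no follow-up condition on release. With no drug effect, a constant hazard, and 10 to 14 days for siltuximab against 30 for controls, the spurious gap is about 22 to 29 points at 50% risk and 10 to 13 at 20%. It is smaller if events come early and absent with equal follow-up. The harm is a misleading descriptive contrast or early public message, not a failed error rate.

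**What to change.** 1. Delete or qualify the assurance in section 11. Report which data reviews were made and why recruitment ended.
2. In 11.2.5, limit any released efficacy comparison to pairs in which both members began ventilation at least 30 days before the data cut, whatever their outcome. Alternatively, compare both groups at the same follow-up time with censoring. Do not define eligibility as having completed 30 days or died, which over-selects deaths.
3. Pick controls from the list of eligible untreated patients by a rule fixed in advance and applied without outcome data. The detail may sit in the analysis plan.

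The cost is protocol wording and a pre-specified matching procedure. A 30-day efficacy comparison has to wait for its pairs to mature. Safety review is not delayed.

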11.1 Sample Size Determination

No statistical sample size estimation was performed. For this study patients from one single center in Italy will be enrolled as follows:

- All patients treated with siltuximab diagnosed with COVID-19 infection who have developed serious respiratory complications, and
- An equal number of case control patients that consented to their data collection.

It is estimated that in total up to 50 patients will be enrolled.

11.2 Statistical Considerations

The primary approach to the statistical analysis will be exploratory using descriptive statistics, exploratory tests and confidence intervals. All data will be presented in by-subject data listings.

11.2.1 Analysis of Demography, Disease Details, Pretreatment, Concomitant Medication, and Other Baseline Data

If not stated otherwise the following standard descriptive analyses will be presented:

11.2.1.1 Descriptive Statistics for Continuous Data

The number of patients (N), mean, standard deviation (SD), minimum, lower quartile, median, upper quartile, and maximum will be presented. These descriptive statistics will be determined for measured values and relevant differences.

11.2.1.2 Descriptive Statistics for Categorical Data

Absolute frequencies and percentages will be presented. For relevant changes from baseline, shift tables may be presented.

11.2.2 Analysis of Treatment Data

In addition to the descriptive statistics previously mentioned, all laboratory parameters will include the value, the reference range (if available), and whether the value was considered clinically significant or not (if available). All information related to COVID-19 and treatment will be presented.

11.2.3 Analysis of Endpoint Data

Data on the endpoints specific for the study cohort considered will also be analyzed by descriptive and exploratory statistical methods. Due to the small sample size statistical comparisons between the siltuximab treatment group and the matched control group will not be performed.

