6 STUDY OBJECTIVES

The is a case control study to observe treatment and collect data on two cohorts of patients treated with siltuximab and a corresponding case control group of patients who have developed severe respiratory complications with COVID-19 infection.

Primary objective

Cohort A: reduction of the need of invasive ventilation or 30-day mortality

Cohort B: reduction of mortality

Secondary objectives

Cohort A

Reduction of the need of time of ventilatory support

Improvement of the lung function

Improvement of radiologic findings

Cohort B

Reduction of days of need of intubation

Percentage of patients that undergo to tracheostomy

Improvement of the lung function

Improvement of radiologic findings

Primary endpoint:

Cohort A: Reduction of the rate of need of invasive ventilation or 30-day mortality

Cohort B: Reduction of length of ICU staying or 30-day mortality

Secondary endpoints:

Cohort A

Reduction of days of need of ventilatory support

Improvement of P/F fraction (resolution of ARDS i.e. P/F>300, or increase from baseline value of at least 50% if P/F>100 or 100% if P/F<100, at day 3, 8 and 15)

Reduction of the duration of invasive ventilation or length of ICU

Improvement of radiologic imaging

Cohort B

Reduction of days of need of intubation

Percentage of patients that undergo to tracheostomy

Improvement of P/F fraction (resolution of ARDS i.e. P/F>300, or increase from baseline value of at least 50% if P/F >100 or 100% if P/F<100, at day 3, 8 and 15)

Improvement of radiologic imaging

Exploratory end points

Correlation of outcomes with IL-6 levels

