8.2 Justification of Study Design

The nature of the study allows for collecting information in a timely manner and will enable the researchers to generate hypotheses about the treatment under the compassionate use program for COVID-19. It is important to assess risk/benefit profile of siltuximab in this indication. A matched consented case control group (one case control per patient) has been included in this study to enable direct comparisons and to provide in-depth safety and efficacy data on siltuximab in the treatment of this patient population.

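### Section 11.2.3 bars statistical comparison with the matched controls, which conflicts with section 11.2 and leaves no between-group difference reported with its uncertainty

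*Protocol*

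**What the plan says.** - **Section 11.2.3 (endpoint data).** Endpoint data "will also be analyzed by descriptive and exploratory statistical methods". The next sentence says that, because the sample is small, "statistical comparisons between the siltuximab treatment group and the matched control group will not be performed".
- **Section 11.2.** The primary approach is "exploratory using descriptive statistics, exploratory tests and confidence intervals". It does not say whether the tests and intervals are within or between groups.
- **Section 8.2.** One matched control per treated patient was included "to enable direct comparisons and to provide in-depth safety and efficacy data on siltuximab". The same section calls the study hypothesis-generating.
- **Section 11, opening text.** Within each cohort, "the analysis will include a descriptive comparison of the siltuximab treatment group and the control group", covering the endpoints and other measurements.
- **Section 6.** The first primary endpoint is "Cohort A: Reduction of the rate of need of invasive ventilation or 30-day mortality". The Cohort B primary endpoint is likewise a reduction, in length of ICU stay or 30-day mortality.
- **Sections 11.2.1.1 and 11.2.1.2.** Categorical data are summarised by counts and percentages. Continuous data are summarised by the usual statistics, for values and for differences judged relevant.

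**The concern.** The statements about comparing siltuximab with control do not fit together. The general section promises exploratory tests and intervals, while the endpoint section excludes statistical comparison. The primary endpoints cannot be read within one group: invasive ventilation, death and length of ICU stay have no within-patient baseline, so a reduction has meaning only against the controls.

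At stake is how the main result is reported. One analyst could follow 11.2 and give an interval for the difference. Another could follow 11.2.3 and decline. The second report would leave readers to judge the difference by eye from two summaries, with no measure of its uncertainty and no account of the pairing. This matters more because section 11 allows intermittent review for efficacy signals and section 11.2.5 allows ad hoc release of results.

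This is not detail left for an analysis plan to supply. It is an explicit protocol rule, which an analysis plan could not reverse without contradicting the protocol.

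**Working it through.** **The plan's own figure.** There is no powered sample size to reproduce: section 11.1 says that none was calculated and estimates a total of up to 50. The synopsis makes half of these treated and half controls, and section 8.1 splits treated patients about 3:1.

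- Treated: 50 × 0.50 = 25, with 25 controls.
- Cohort A: 25 × 0.75 = 18.75, about 19 pairs.
- Cohort B: 25 × 0.25 = 6.25, about 6 pairs.

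These are ceilings, because 50 is a maximum.

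**Unpaired 95% half-width of a risk difference:** 1.96 × √[p₁(1−p₁)/n + p₂(1−p₂)/n]. The protocol gives no event rates, so the risks below are assumptions (control / siltuximab).

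| Assumed risks | A, n = 19 | B, n = 6 |
|---|---|---|
| 50% / 50% | 0.318 | 0.566 |
| 50% / 30% | 0.305 | 0.543 |
| 50% / 25% | 0.297 | 0.529 |
| 60% / 30% | 0.302 | 0.537 |
| 40% / 20% | 0.284 | 0.506 |

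The first row worked through: 1.96 × √(0.50/19) = 0.318 and 1.96 × √(0.50/6) = 0.566. The range is 28 to 32 points in A and 51 to 57 in B. The normal approximation is rough at n = 6.

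**Paired 95% half-width:** 1.96 × √[(d − RD²)/n], where d is the assumed share of discordant pairs and RD the risk difference.

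| d, RD | A, 19 pairs | B, 6 pairs |
|---|---|---|
| 0.3, 0.2 | 0.229 | 0.408 |
| 0.5, 0.2 | 0.305 | 0.543 |
| 0.5, 0 | 0.318 | 0.566 |

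The paired range is about 23 to 32 points in A and 41 to 57 in B. If matching makes pairs alike, respecting it narrows the interval, though not enough to make Cohort B informative.

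**Is the stated reason sound for tests?** For the four unequal risk pairs in the first table, approximate two-sided 5% power is 24% to 46% in A and 10% to 17% in B. In B an exact McNemar test falls below 0.05 only if all six pairs are discordant in the same direction: 2 × 0.5⁶ = 0.031, whereas five give 2 × 0.5⁵ = 0.0625. So the premise of 11.2.3 is correct as a reason not to rely on hypothesis tests. It does not prevent an interval from being computed, and the width of that interval is what a reader needs to know.

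**The case against.** The strongest defence is that the study is declared exploratory, that 11.2 is a general statement and that 11.2.3 is the specific rule for endpoints. On that reading every analyst omits between-group tests, and the only open question is whether the rule also excludes an interval for the difference. The comparisons in 8.2 may simply be the descriptive ones planned in section 11. No error rate, sample size or confirmatory claim depends on the sentence.

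Much of this stands. The tension with 8.2 is soft. The tests and intervals in 11.2 could be within-group, so the conflict there is real but not absolute.

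Three stronger readings are tempting and not supported:

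- **That the reduction endpoints have no estimate at all.** Section 11 plans group summaries side by side, from which a crude difference follows.
- **That results will carry no intervals of any kind.** Intervals within each group are compatible with both 11.2 and 11.2.3.
- **That the protocol discards the matching.** It does not say so; it only commits to no between-group estimate that would use it.

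What the defence does not answer is that an interval within one group cannot address a reduction relative to controls. Even on the general-plus-specific reading, the difference that the primary endpoints describe would be reported without its uncertainty.

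**Conclusion.** The concern holds in a limited form. Section 11.2.3 conflicts with 11.2 and sits poorly with 8.2 and with the wording of the primary endpoints. Followed literally, it yields a primary result with no interval on the between-group difference and no account of the 1:1 matching.

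Small size justifies withholding confirmatory claims. It does not justify withholding an interval that would be about ±30 points wide in Cohort A and ±55 in Cohort B. Those figures rest on the full 50 patients, the 3:1 split, assumed risks of 20% to 60%, and an unpaired normal approximation.

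This should be fixed before analysis. It does not invalidate the study, which makes no confirmatory claim.

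**What to change.** Replace the last sentence of 11.2.3 with text such as:

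> No confirmatory hypothesis tests will be performed. For each cohort, between-group differences in the primary endpoint will be reported as exploratory estimates with 95% confidence intervals that respect the matched pairs: a paired risk difference with a small-sample or exact interval for invasive ventilation or 30-day mortality (Cohort A) and for 30-day mortality (Cohort B), and a paired difference in length of ICU stay for that component of Cohort B, reported alongside mortality. Cohort B will not support a conclusion on mortality reduction.

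ICU stay needs its own measure because it is not a risk. It should be shown with mortality because an early death also shortens the stay. A Cox model with pair-clustered variance is not advised: with about 6 clusters in B, and even with 19 in A, that variance is unreliable and tends to understate uncertainty.

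Align 8.2, the opening of section 11 and 11.2 with the new text, stating that the comparisons are exploratory and between matched groups.

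Cost: one paragraph, little extra analysis and no new data. Section 13.3 requires Ethics Committee agreement to the modification. The visible price is wide intervals in the report, which is an accurate picture of what the study can show.
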